7.1.7.1 Primary safety endpoint: Rate of common complications during 360-day post operation

Note: Common complications include (as shown in the following table)

SN.	Name	SN.	Name
1	Occluder displacement	5	Residual shunt above medium
2	High-grade atrioventricular block	6	Intractable headache or migraine
3	Cardiac tamponade	7	Cerebral embolism

4	Air embolism		
---	--------------	--	--

The definitions of common complications are as follows:

- (1) Occluder displacement: refers to displacement of occluder to right atrium, right ventricular outflow tract, main pulmonary artery, left atrium, etc. due to special anatomical position of ASD, selection of too small occluder resulted from incorrect measurement and improper operation, etc.
- (2) High-grade atrioventricular block: means that there are two or more continuous supraventricular excitations (generally sinus P waves) that cannot be transmitted down to the ventricle at an "appropriate" atrial rate (≤ 135 bpm), and this conduction barrier must be caused by block rather than interference induced by connection or ventricular ectopic pacing points.
- (3) Cardiac tamponade: refers to cardiac compression, ventricular filling obstruction and a series of hemodynamic abnormalities, such as venous pressure increase and even cardiogenic shock, due to the rapid accumulation of fluid in pericardial cavity.
- (4) Air embolism: refers to inadvertently injection of air into coronary artery due to improper operation of occluder implantation. Air embolism can temporarily block blood flow in coronary artery, which may lead to acute myocardial infarction, angina pectoris, arrhythmia and cardiac arrest.
- (5) Residual shunt above medium: left-to-right shunt signal with diameter ≥ 5 mm, judging from Doppler left-to-right signal.
- (6) Intractable headache or migraine: refers to the syndrome with recurrent headache as the main symptom, which may have aura and accompanying symptoms.
- (7) Cerebral embolism: refers to various emboli (such as endocardial mural thrombus, atherosclerotic plaque, fat, etc.) that enter the cerebral artery with blood flow and block blood vessels, which will cause ischemic necrosis of brain tissue in the blood supply area of the artery and result in focal neurological deficit when collateral circulation cannot be compensated.

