7.1.6 Efficacy evaluation method

7.1.6.1 Primary efficacy endpoint and corresponding evaluation, recording and analyzing method and time

Effective closure rate at 360-day post operation

Evaluation time: 360-day post operation

Definition of effective closure: no or only mild-small residual shunt (judging from left-to-right Doppler signal, left-to-right shunt signal with diameter < 5 mm) observed by TTE or TEE after device implantation.

Evaluation method: TEE or TTE

7.1.6.2 Secondary efficacy endpoint and corresponding evaluation, recording and analyzing method and time

Immediate operation success rate

Evaluation time: Immediately post operation

Immediate operation success means that left and right disks are effectively fixed on left and right sides of atrial septum respectively and smoothly released without displacement or migration and the delivery system is successfully withdrawn;

Note: the displacement and migration can be judged by observing whether the position of markers is the same as that before release under DSA, and whether the left and right discs are located on both sides of the atrial septum under TEE or TTE.

7.1.7 Safety endpoints and corresponding evaluation, recording and analyzing method and time:

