8.2 Sample size calculation

8.2.1 Total sample size

This clinical trial plans to recruit 146 subjects. The sample size determination process is as follows:

This clinical trial adopts single-arm OPC design and uses effective closure rate at 360-day post operation and the rate of common complications during 360-day post operation as the basis for sample size estimation.

[figure not shown]
At present, the technique of ASD occlusion is mature and widely used in clinic. A large number of clinical data, large-scale clinical trials, randomized controlled trials and systematic evaluations (Meta analyses) of traditional metal products on the market have proved the safety and efficacy of this treatment (advantages compared with the surgery). The literature data are shown in the table below.

Clinical Trial to Evaluate the Safety and Efficacy of Absnow™ Absorbable ASD Closure System for ASD Patients

[figure not shown]
Literatures	Publishing date	Device name	Effective closure rate at 360-day post operation	Rate of common complications during 360-day post operation	Sample size
Zhong-Dong Du, et al. ^[1]	2002	Amplatzer Septal Occluder	98.5%	0.65%	288
Shinichi Oho, et al. ^[2]	2002	Amplatzer Septal Occluder	97%	2.86%	35
Sergio Luiz Navarro Braga, et al. ^[3]	2004	Amplatzer Septal Occluder	95.8%	4.1%	49
Cristiano Oliveira Cardoso, et al. ^[4]	2006	Amplatzer Septal Occluder	93%	3.96%	101
Thomas K. Jones, et al. ^[5]	2007	GORE HELEX Septal Occluder	98.1%	3.4%	119
Allen D. Everett, et al. ^[6]	2009	Amplatzer Septal Occluder	96%	0.9%	478
Tehmina Kazmi, et al. ^[7]	2009	Amplatzer Septal Occluder	99%	3.5%	204
Alexander J. Javois, et al. ^[8]	2014	GORE HELEX Septal Occluder	96.7%	--	137
Sukman T. Putra, et al. ^[9]	2015	Amplatzer Septal Occluder & Lifetech Heart ASD occluder	96.37%	2.6%	152
Daniel R. Turner, et al. ^[10]	2017	Amplatzer Septal Occluder	98.21%	1.6%	1000

1) Effective closure rate at 360-day post operation

Combining (Meta-analysis) of the one-year effective closure rates reported in each of the above documents shows that the one-year treatment success rate of the traditional metal ASD closure system is 98%, and the 95% CI is [97%, 99%].

[figure not shown]

Combining (Meta-analysis) of the lower limits of 95% CI of one-year effective closure rates of each of the above documents shows that 95% CI of lower limits of 95% CI of one-year effective closure rates of traditional metal ASD closure system is [94%, 97%].

[figure not shown]

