method = normal
nullproportion = 0.94
proportion = 0.99
sides = U
power = 0.8
alpha = 0.025
ntotal = . ;
run;↵
```

The POWER Procedure
Z Test for Binomial Proportion

Fixed Scenario Elements	
Method	Normal approximation
Number of Sides	U
Null Proportion	0.94
Alpha	0.025
Binomial Proportion	0.99
Nominal Power	0.8
Variance Estimate	Null Variance

Computed N Total	
Actual Power	N Total
0.802	121

The target and OPC of effective closure rate at 360-day post operation are set as 99% and 94%, respectively. SAS software calculation indicates that at least 121 patients are needed. Considering a dropout rate of 20%, 146 patients are required.

b) Rate of common complications during 360-day post operation

```
proc power;
onesamplefreq
test = z
method = normal
nullproportion = 0.06
proportion = 0.01
sides = L
power = 0.8
alpha = 0.025
ntotal = . ;
run; ↵
```

The POWER Procedure
Z Test for Binomial Proportion

Fixed Scenario Elements	
Method	Normal approximation
Number of Sides	L
Null Proportion	0.06
Alpha	0.025
Binomial Proportion	0.01
Nominal Power	0.8
Variance Estimate	Null Variance

Computed N Total	
Actual Power	N Total
0.802	121

The target and OPC of rate of common complications during 360-day post operation are set as 1% and 6%, respectively. SAS software calculation indicates that at least 121 patients are needed. Considering a dropout rate of 20%, 146 patients are required.

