8.3 Significance level and power

This trial adopts single-arm design and the significance level α (one-sided) = 0.025, and the power is 80%.

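### Closure failure at day 360 counts in both co-primary endpoints, so the 1% complication target sits at its floor and the stated 80% power leaves almost no margin for other complications

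*Protocol*

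**What the plan says.** - **Efficacy.** Protocol 7.1.6.1 defines effective closure as "no or only mild-small residual shunt (judging from left-to-right Doppler signal", with a signal diameter below 5 mm, assessed at day 360.
- **Safety.** Protocol 7.1.7.1 lists seven common complications. The fifth is "Residual shunt above medium: left-to-right shunt signal with diameter" of 5 mm or more, on the same Doppler measure. The schedule in 7.2.2 collects common complications at Visits 1 to 5, and Visit 5 is the day-360 visit.
- **Planning values (8.2.1).** "The target and OPC of effective closure rate at 360-day post operation are set as 99% and 94%, respectively". "The target and OPC of rate of common complications during 360-day post operation are set as 1% and 6%, respectively". Each endpoint is sized on its own, and for each "SAS software calculation indicates that at least 121 patients are needed". Section 8.3 gives a one-sided level of 0.025 "and the power is 80"%.
- **Decision.** Protocol 8.1 and 8.5 and SAP 5.1.2 require both endpoints to meet their limits. SAP 5.1 makes the FAS the primary set for both and uses exact 95% intervals. SAP 4.2 imputes missing day-360 data as ineffective closure and as a complication.
- **Literature (8.2.1).** Pooled one-year closure is 98% and pooled one-year complications are 1%.

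Neither document mentions that the two endpoints overlap, and neither gives a power for the joint decision.

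**The concern.** Below 5 mm and 5 mm or above are complements. For a subject with a day-360 echo, failing efficacy means having complication 5. If 99% close, about 1% already have a safety event, and that is the whole safety target. Two kinds of patient would push the rate above plan: one whose defect is effectively closed but who has any of the other six complications, and one with a shunt of 5 mm or more at an earlier visit that has closed by day 360.

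The pooled literature pair, 2% non-closure with 1% complications, is not possible under the trial's own definition, so the 1% target seems to come from a narrower quantity. At stake is the stated power of the overall conclusion, and how the safety result is read when closure failure is one of its components.

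**Working it through.** **1. Reproduce the plan's figure.** Inputs from 8.2.1: p0 = 0.06, p1 = 0.01, one-sided alpha 0.025, power 0.80, z test with null variance.

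n = [(1.960·√(0.06·0.94) + 0.842·√(0.01·0.99)) / 0.05]² = 120.65, so 121. Power at 121 is 0.802. The efficacy calculation is the mirror image and gives the same result. The sample-size arithmetic is correct as printed.

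**2. Overlap.** Let F be the number of closure failures and C the number of subjects with any common complication. With complication 5 as the complement of effective closure, and missing data counted as failure on both, F ≤ C. The limits mirror each other, so both tests allow the same number of events, c. Then P(F ≤ c and C ≤ c) = P(C ≤ c): joint power equals safety power. A simulation at n = 121, with 1% non-closure plus 0.5% other events, gave 88% for efficacy, 73% for safety and 73% jointly.

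**3. Exact rule (SAP 5.1.2).** The upper limit of the Clopper-Pearson 95% interval must be below 6%.

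| n | events allowed | upper limit at that count | upper limit with one more |
|---|---|---|---|
| 121 | 2 | 5.84% | 7.07% |
| 142 (SAP) | 2 | 5.00% | 6.05% |
| 146 (protocol) | 3 | 5.89% | 6.87% |

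**4. Power by total complication rate.** The total is 1% non-closure plus q, where q is the share of patients with a safety event but effective closure at day 360. The documents give no value for q, so it is an assumption shown as a range. Exact power is the binomial probability of at most c events, with no missing data.

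| total rate | z formula, n = 121 | exact, n = 121 | exact, n = 142 | exact, n = 146 |
|---|---|---|---|---|
| 1.0% (q = 0) | 80% | 88% | 83% | 94% |
| 1.5% (q = 0.5%) | 60% | 73% | 64% | 82% |
| 2.0% (q = 1%) | 43% | 56% | 46% | 67% |
| highest rate keeping 80% | 1.005% | 1.27% | 1.08% | 1.58% |

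Example at n = 121 and 2%: 0.0868 + 0.2143 + 0.2624 = 0.563 for 0, 1 and 2 events.

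A total of 2% is also the minimum implied by the pooled 98% closure, with no other complication at all.

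**5. Literature table.** Nine rows give both rates. Complications are nominally below 100% minus closure in seven. Two of these are explained by rounding or denominators:
- n = 35: 1/35 = 2.86% and 34/35 = 97.1%, printed as 97%.
- n = 49: 2/49 = 4.1% and 46/48 = 95.8%.

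The other five are:

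| n | non-closure | complications |
|---|---|---|
| 288 | 1.5% | 0.65% |
| 101 | 7% | 3.96% |
| 478 | 4% | 0.9% |
| 152 | 3.63% | 2.6% |
| 1000 | 1.79% | 1.6% |

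The gap in the last row is only 0.19 points.

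**The case against.** Several stronger readings are tempting, and the documents do not support them.

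- **That the 99%/1% pair is impossible, or leaves no room for the other six complications.** The endpoint is a rate of patients. A displacement or embolism in someone who also fails closure adds nothing. The pair is attainable but lies on the boundary.
- **That 80% power is lost as soon as any other complication occurs.** This is close to true only for the protocol's z formula at 121. The exact rule keeps 80% up to 1.27%, 1.08% or 1.58%, and at 146 subjects it still gives 82% at a total of 1.5%.
- **That every closure failure is a complication, so a safety pass guarantees an efficacy pass.** FAS group (b) includes device-caused implant failures, even with no device in the body, and the documents do not settle whether an untreated defect is a residual shunt. An echo after day 360, within the 30-day window, may fall outside the safety period. Protocol 8.9 also names the FAS as the main set for primary safety in item (1) but bases safety evaluation on the SS in item (4). SAP 4.1.2 and 5.1 settle on the FAS.
- **That the literature column is proven to be a different endpoint.** Closure denominators and the studies' event definitions are not shown. The evidence is strong but indirect.

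It is also fair to say that the printed arithmetic is right, that type I error and the decision rule are untouched, and that 8.3 does not call its 80% a joint power. The exact figures at 142 and 146 assume no missing data; under the SAP's imputation each missing subject is an event on both endpoints, which is a separate difficulty.

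**Conclusion.** The point stands as an undisclosed overlap combined with an optimistic safety target; it is not an arithmetic error. For subjects with a day-360 echo, and for imputed missing data, a closure failure is also a safety event. The 1% target is therefore the floor implied by 99% closure, and the power of the joint decision is essentially the safety power.

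The margin above that floor is thin: 80% power is lost once roughly 0.1% to 0.6% of patients (exact rule, depending on n) have a safety event despite effective closure at day 360, and almost at once by the z formula. With an additional 1%, power is 46% to 67% by the exact rule and 43% by the z formula. These figures rest on assumed values of q and on complete data. The consequence is a higher chance than stated that an acceptable device misses the criterion. It does not raise the chance of a false pass.

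**What to change.** **Protocol 8.2.1 and 8.3.** Set the safety planning rate as 1% non-closure plus an explicit, justified allowance for safety events in patients effectively closed at day 360. State the overall power at that rate for the existing sample size. Relabel the literature complication column, or recompute it so that it matches the seven-component composite.

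**SAP 5.1.2.** State that closure failure at day 360 counts in both endpoints. Add, as a supportive safety result, the rate and exact 95% CI of the composite without residual shunt of 5 mm or more. Do not write that a safety pass implies an efficacy pass, given the exceptions above.

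**Cost.** Wording, one extra table, and a less favourable stated power. The decision rule does not change and no patients are added. If the sponsor instead wished to keep 80% by the protocol's own formula, it would need 160 evaluable subjects at a total of 1.5% and 213 at 2%; that is a separate choice and is not required here.

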7.2.3 Visit items

7.2.3.1 Medical history and vital signs

Demographic data, current medical history, past medical history and vital signs will be collected.

- (1) Demographic data: sex, date of birth, height and weight
- (2) Vital signs: blood pressure, pulse, body temperature and respiration
- (3) Current medical history: symptom duration and admission time
- (4) Past history: history of allergy, history of dysfunction of important organs (heart, lung, liver and kidney), and history of surgery
- (5) Medication records: CRF only records anticoagulants, antiplatelets and antibiotics

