7.2.4.3 Visit 2 (30 ± 7 days post operation, outpatient visit)

- (1) Vital signs
- (2) Echocardiography
- (3) ECG
- (4) Medication record

(5) Common complications

(6) AE

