Appendix 2: Headache questionnaire and evaluation

This questionnaire is used to express how you feel about headache and the negative impact of headache on your life. Please choose one answer from five choices.

1. When you have a headache, how often does severe pain occur?

A. Never B. Seldom C. Sometimes D. Often E. Always

2. Does the headache limit your ability to daily activities, such as housework, work, school, or social activities?

A. Never B. Seldom C. Sometimes D. Often E. Always

3. Do you often wish to lie down when you have a headache?

A. Never B. Seldom C. Sometimes D. Often E. Always

4. In the past 4 weeks, do you often feel tired due to headache and feel powerless in work or daily activities?

A. Never B. Seldom C. Sometimes D. Often E. Always

5. In the past 4 weeks, do you often feel bored and restless due to headache?

A. Never B. Seldom C. Sometimes D. Often E. Always

6. In the past 4 weeks, have you been unable to concentrate on work and daily activities due to headache?

A. Never B. Seldom C. Sometimes D. Often E. Always

Evaluation:

Choose A: 6 scores, choose B: 8 scores, choose C: 10 scores, choose D: 11 scores, choose E: 13 scores.

Add up the corresponding points for all the answers.

Total score range: 36 - 78

Level 1: ≤ 49 , no or minor impact

Level 2: 50-55, moderate impact

Level 3: 56-59, significant impact

Level 4: ≥ 60 , seriously impact

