Appendix 3: MIDAS Migraine Questionnaire and score

Five questions were asked to assess the time lost (days) due to migraine over a three-month period. The time loss mainly means paid work, household work, family and social activities. The MIDAS score is obtained by adding all days lost.

1. In the past 3 months, how many days have you been unable to go to work or school due to headache?

_____ Days

2. In the past 3 months, how many days have you partially affected your work or study due to headache (efficiency was decreased by more than half)?

_____ Days

3. In the past 3 months, how many days have you been unable to do housework due to headache?

_____ Days

4. In the past 3 months, how many days have you partially affected your housework due to headache (efficiency was reduced by more than half)?

_____ Days

5. In the past 3 months, have you missed visiting friends and relatives, parties, entertainment such as watching TV, playing cards and other similar activities due to headache?

_____ Days

Total days: _____ Days

Score definition of MIDAS Migraine Disability Assessment Questionnaire

Grading	Degree	Disable Level	Suggestion
0-5	I	Slight or infrequent impact	
There is little need for medical intervention. Simple symptomatic treatment can be used with OTC drugs when seizures occur, but the following conditions should be noted:
 
 1. Evaluate the impact of days off due to headache on subjects' life 2. Subjects with infrequent but severe headache need regular treatment 3. Subjects whose headaches are not effectively relieved by painkillers alone need standardized treatment

6-10	II	Mild or frequent impact	Subjects usually have headache for a long time or severe degree, which cannot be completely relieved by analgesic alone and has obvious influence on life. Standardized treatment is needed in the acute phase.
11-20	III	Moderate impact	Headache has serious influence on life. Standardized treatment is needed in the acute phase.
>21	IV	Serious impact	Need preventive treatment.

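### The headache or migraine component of the primary safety endpoint has no pre-implant baseline and no new-or-worse condition, so pre-existing headache can be counted against the 6% criterion

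*Protocol*

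**What the plan says.** Protocol 7.1.7.1(6) defines the component: "Intractable headache or migraine: refers to the syndrome with recurrent headache as the main symptom, which may have aura and accompanying symptoms". The definition describes a condition. It does not ask for onset after the operation, worsening, or a link to the device.

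Protocol 13.1.4.1(6) says how it may be judged. If a subject complains of headache or migraine, a headache score above 2 or a MIDAS score above 1 may be taken as intractable. Both are absolute cut-offs.

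The two instruments look back over different periods. MIDAS (Appendix 3) covers three months, for example "In the past 3 months, how many days have you been unable to go to work or school due to headache". In the headache questionnaire (Appendix 2), items 4 to 6 cover four weeks, for example "In the past 4 weeks, do you often feel tired due to headache and feel powerless in work or daily activities"; items 1 to 3 state no period.

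Before implantation, Protocol 7.2.3.1 collects "Past history: history of allergy, history of dysfunction of important organs (heart, lung, liver and kidney), and history of surgery". Current history is symptom duration and admission time. Neither the schedule in 7.2.2 nor the preoperative list in 7.2.4.1 contains a headache item, and migraine does not appear among the exclusions in 7.1.5.2. Common complications are first assessed at Visit 1, before discharge, and next at "Visit 2 (30 ± 7 days post operation, outpatient visit".

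SAP 3.2.1 repeats the component's name without a rule for pre-existing headache. SAP section 4 takes baseline as the last valid value before implantation, and for headache none is scheduled. SAP 5.1.2 passes safety if the exact two-sided 95% upper limit is below 6%, and requires both primary endpoints to pass. SAP 4.2 imputes incomplete safety follow-up as a complication.

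**The concern.** A subject with long-standing migraine can satisfy the definition and the cut-offs without any change after the device is placed. At the first two visits, part or most of the MIDAS recall period lies before the operation, so lost days that precede the device can contribute to the score. The component then mixes background headache with any effect of the procedure, and no planned baseline measurement separates them.

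The bias runs against the device. It raises the risk that an acceptable device misses a co-primary endpoint, and it makes a real effect on headache harder to see. It matters because the pass rule tolerates only two or three events. With no written rule, sites may also decide differently whether an old headache is an event.

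**Working it through.** **Inputs.** OPC "nullproportion = 0.06" and target "proportion = 0.01", one-sided 0.025, power 80% (Protocol 8.2.1). Planned size 146 in the protocol ("Considering a dropout rate of 20%, 146 patients are required") and 142 in SAP 3.1; both are carried. Pass rule from SAP 5.1.2. The share q of subjects counted only because of prior headache is not in the documents and is assumed to lie between 0 and 5%.

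**Step 1: the plan's own figure.** For the z test with null variance,

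n = [(1.960·√(0.06·0.94) + 0.842·√(0.01·0.99)) / 0.05]² = 120.65, so 121, with power 0.802.

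This reproduces the protocol. 121 × 1.2 = 145.2, rounded up to 146.

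**Step 2: event budget.** The Clopper-Pearson upper limit for x events in n is the 0.975 quantile of Beta(x + 1, n − x).

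| n | Most events that pass | Upper limit | One more event |
|---|---|---|---|
| 146 | 3 | 5.89% | 6.87% |
| 142 | 2 | 5.00% | 6.05% |
| 121 | 2 | 5.84% | 7.08% |

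So 4 of 146 (2.7%) or 3 of 142 (2.1%) subjects counted for prior headache would fail the test with no other complication.

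**Step 3: chance of passing.** Per-subject rate p = 1 − (1 − 0.01)(1 − q), which is 1.99% at q = 1% and 2.98% at q = 2%. The chance of passing is the binomial probability of no more events than the budget, with no missing follow-up.

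| n | q = 0 | 0.5% | 1% | 2% | 5% |
|---|---|---|---|---|---|
| 146 | 94% | 82% | 67% | 36% | 2% |
| 142 | 83% | 64% | 46% | 20% | 1% |
| 121 | 88% | 73% | 57% | 30% | 2% |

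**Step 4: how far recall reaches before the operation** (three months taken as 90 days, four weeks as 28).

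| Visit | MIDAS | Appendix 2, items 4–6 |
|---|---|---|
| 1, before discharge | nearly all | nearly all |
| 2, days 23–37 | 90 − 37 = 53 to 90 − 23 = 67 days | 28 − 23 = 5 days at the earliest, none at day 30 |
| 3, days 76–104 | 90 − 76 = 14 days at the earliest, none at day 90 | none |
| 4 and 5 | none | none |

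The overlap is material at Visits 1 and 2 for MIDAS and mainly at Visit 1 for Appendix 2. After that, only the missing baseline matters: migraine that simply continues still fits the definition.

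**Step 5: the cut-offs affect q.** The Appendix 2 total runs from 36 to 78, so a raw score above 2 is always reached; read as a level, it means levels 3 and 4 (56 or more). A MIDAS raw score above 1 means two or more days; read as a degree, it means degree II upward (six or more days). The protocol does not say which reading applies, so the documents cannot narrow q.

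**The case against.** The strongest reply is that investigators would not record an unchanged old migraine. Protocol 13.1 lists common complications among adverse events, and describes adverse events as arising during the trial. SAP 6.1 speaks of treatment-emergent events. A reader might infer from the component's definition that pre-existing migraine is always counted; the documents do not say that. They also do not say the reverse. The treatment-emergent wording is undefined and is not applied to the primary safety endpoint. What stands is that prior headache can be counted, and that the decision is left to unwritten judgement.

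Second, a reader might take the questionnaires to be given routinely at Visits 1 to 5. They are not in the schedule; 13.1.4.1(6) brings them in only after a complaint, and permissively. That limits the number of cases, but three or four are enough to fail.

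Third, three-month recall belongs to MIDAS alone, and its effect is largely gone by Visit 3.

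Fourth, the steep fall in Step 3 reflects the small event budget as much as headache. By the same formula, 2% of subjects with incomplete follow-up, imputed as events under SAP 4.2, would give the same 20% or 36% with no headache cases. This is correct: the two sources draw on one allowance.

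Fifth, the bias is conservative with respect to approval. That is also correct, and is why this is a weakness to repair rather than a threat to the type I error rate.

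**Conclusion.** The concern holds in this form: the component has no new-onset or worsening condition, uses absolute scores, and has no scheduled pre-implant headache record, so pre-existing headache can be counted as a complication. The missing baseline is the main defect; recall adds to it mainly at Visits 1 and 2.

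The event limits in Step 2 follow directly from the SAP rule. The pass probabilities rest on an assumed q, a true rate of 1%, independence of the two sources and complete follow-up. The gap between the 142 and 146 rows comes from the different planned sizes in the two documents, not from headache.

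A reader might go further and say that the comparison with the 6% criterion is uninterpretable, or that background headache could never be separated afterwards. The documents do not support either. They do not show how the literature behind the criterion handled prior headache, and Protocol 8.2.1 says the value also drew on clinical experience and this trial's endpoint definitions. The case report form is not shown, and site records may hold some headache history. The change should be made, because a baseline is cheap before implantation and cannot be reliably recovered later.

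**What to change.** - **Screening.** Give Appendices 2 and 3 once in the preoperative window (−30 to 0 days), and add a headache or migraine item to past history in Protocol 7.2.2, 7.2.3.1 and 7.2.4.1.
- **Definition.** In Protocol 7.1.7.1(6) and the SAP, count the component only if headache is new after implantation or in a worse questionnaire grade than at screening. State whether the cut-offs in 13.1.4.1(6) are levels or raw scores.
- **Recall.** Where the window crosses the implant date (Visits 1 and 2, and an early Visit 3 for MIDAS), compare with the screening grade and do not count a subject on pre-operative days alone. Do not shorten MIDAS to days since the operation while its day-count cut-offs stay the same; that would make genuine early headache harder to register.
- **Transparency.** List all subjects who meet the absolute cut-off, whether or not they are counted, so that the effect of the rule can be seen.

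The cost is two short questionnaires at an existing visit, one page in the electronic case report form, and wording changes in both documents. The downside is that a subject already in the top grade at screening cannot register worsening by grade.
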